Visits and exams	
Every prostate cancer patient consecutively evaluated at the recruiting Centers and planned to receive radical exclusive or post-operative radiotherapy will be registered; this registration includes demographic and staging results data.
 
Only intermediate, high, very high patients will have, however, treatment and follow up CRF compiled, based on the inclusion criteria
 
Eligible patients will then receive all the information necessary to formulate their adhesion to the study and finally the physician will fill in the “Pretreatment” CRF that will include: Demographic Information; Anamnestic data; Initial diagnosis (date; PSA at diagnosis); Risk factors; Staging; Quality of life and symptoms caused by prostate cancer; General quality of life;
 
The choice of the treatment will be done based on commonly used international guidelines and on the specific internal protocol of each participating Center.
 
Since this study is observational, involved patients will be treated following good clinical practice and institutional policies procedures.
 
Clinical outcomes and variables, demographic features, dosimetric analysis and acute/late toxicities of both RT (with and without ENI) and ADT will be reported.

	
Follow-up visits on 1,3,6,12/18,24/30 and 36 months
 
Every patient will be contacted by the physicians to fill a CRF that will include: Vital state (mortality, date and causes of death) or loss to follow up; Last PSA value; Other treatments (drugs); type of RT and ADT treatment Acute and late toxicities; Biochemical Relapse with PSA value and date of last PSA; Quality of life and symptoms due to prostate cancer; General quality of life.
 
Survival status (mortality, date and cause of death) or exit from the study; If macroscopical recurrence or disease progression will occur, the radiological exams (if performed) will be reported; Further treatments received/planned after radiotherapy; The last available PSA;
 
Acute/Late toxicity
 
Genitourinary and gastrointestinal toxicity due to radiation therapy.
 
A CRF will be completed regarding: Technical characteristics of the radiation treatment; Quality of life and complications due to prostate cancer; General quality of life

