In the adjuvant setting, sterilizing microscopic disease potentially persistent after radical surgery, particularly in high-risk patients, represents the rationale of adding WPRT to prostatic bed radiotherapy in pN0 patients. Goldner et al. evaluated the clinical impact of prostate only adjuvant RT in pN0 patients showing a 5-year biochemical relapse free survival of 100% and 58% in patients with a risk of nodal involvement <15% and >15%, respectively. These findings may be explained by a microscopic involvement of pelvic structures (lymph nodes, bone) other than prostate bed. However, the role of adjuvant post-surgical WPRT need to be validated by large prospective studies, not actually ongoing to our knowledge. [37, 38, 39, 40]. Moreover, no clear-cut guidelines are available about the usefulness of adding ADT to adjuvant RT in the different subsets of pN0 patients.

On the other hand, nodal involvement (pN1) is a strong negative prognostic factor and adjuvant RT in these patients may be useful to optimize loco-regional control deferring first or second line systemic therapies [41]. Actually, the standard adjuvant treatment for pN1 PCa patients is represented by long term ADT, but the association with WPRT might significantly increase survival outcomes [42]. A recent analysis conducted by SEER on “pN1 M0” PCa patients treated with adjuvant WPRT seems to confirm the benefit obtained by the association of WPRT with ADT, demonstrating a survival advantage for intermediate risk patients [43].

Conclusions, rationale and summary of the study

In conclusion, open questions about ENI for prostate cancer still remain:

1. In the exclusive radiotherapy scenario, does ENI produce an overall or biochemical relapse free survival advantage over prostate only radiotherapy for intermediate/high/very high risk cases?
2. If ADT is added to prostate only radiotherapy, in intermediate/high/very high risk cases, ENI is any longer needed?

3. Is ENI, associated or not to ADT, linked with an OS or bRFS survival advantage in patients submitted to adjuvant postsurgical prostate radiotherapy?
4. Additional toxicity due to the larger volumes treated might be reduced by more sophisticated radiotherapy techniques when ENI is added to prostate?
5. How many Radiation Oncology centers use ENI to treat patients with intermediate/high/very high-risk prostate cancer, with or without ADT?

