We propose a no-profit, multicenter observational study to collect data of consecutive patients treated with ENI both in the exclusive radical radiotherapy scenario and in the adjuvant postsurgical setting. Cases treated both with and without associated ADT will be recruited to evaluate Overall survival (OS) (that will be the main endpoint), Cause-specific (CSS) and Biochemical Relapse Free survival (bRFS), toxicity and Quality of Life (QoL) (the secondary endpoints).

Aims of the study

Clinical features and outcomes will be assessed as better detailed in the following lines:

1. To define the diffusion of the practice of treating pelvic lymph-nodes in patients affected by intermediate/high/very high risk non-metastatic prostate cancer (PCa) among Italian Radiation Oncology Centres, submitted to radical or post-operative radiotherapy;
2. To define the diffusion of the different radiotherapy techniques used to treat pelvic nodes and the other features of the radiation treatment;
3. To register prospectively biochemical and clinical failure, prostate cancer deaths and deaths for any cause in the population studied;
4. To register prospectively the toxicity due to radiotherapy and androgen deprivation therapy in patients treated with pelvic nodes radiotherapy;
5. To compare clinical outcomes and toxicities observed in the different clinical and therapeutic subgroups with the corresponding historical data relative to PCa patients treated with radiotherapy with or without elective pelvic nodal irradiation, already available in the existing AIRO (Italian Society of Radiation Oncology) databases;

6. To exploit the collected data to define the need and the features of a prospective randomized trial evaluating the efficacy of elective pelvic nodal irradiation in patients with intermediate/high/very high risk non-metastatic prostate cancer.
7. The data obtained from the present observational study will be helpful for designing a subsequent randomized controlled trial.

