In summary, the study aims at the definition of survival, toxicity and QoL data in a representative sample of intermediate, high and very high risk prostate cancer patients consecutively recruited in Italian Radiation Oncology Centres over two years. Parameters considered will be OS, CSS and bRFS, toxicity (rectal, bladder, bowel toxicity, according to CTCAE v.4 scale) and QoL (according to the SF-12 scale and UCLA-PCI scale). Primary end point will be OS. Secondary endpoints will be CSS, bRFS, gastrointestinal and genitourinary toxicity, QoL deterioration.

Study Design

This is a prospective, multicenter, observational cohort study aimed to describe the advantage/disadvantage of different treatments of patients with intermediate/high/very high risk prostate cancer, through a web-based database.

Study Duration

The recruitment period, taking into account the needed sample size (*v.infra*) will be of two years, followed by three-year follow up period for each patient, with an accrual of at least 400-500 patients.

Population, Procedures

The study will include all consecutive patients affected by intermediate, high or very high-risk prostate cancer that fit the inclusion criteria and who are evaluated at each Centre involved in the study. Patients may have already undergone or not to radical prostatectomy and/or pelvic lymphadenectomy.

Inclusion criteria

- Men older than or aged 18 years;
- Histologically confirmed intermediate, high or very high risk prostate cancer patients (NCCN classification: Intermediate Risk T2b and T2c or Gleason Score 7 or PSA value between 10 and 20 ng/mL; High risk: T3a or Gleason score 8-10 or PSA > 20 ng/ml; Very high risk: T3b-T4 or patients with multiple adverse risk factors reported in the high risk category that may be shifted in the very high risk group
- Patients eligible for -and actually submitted to- radical radiotherapy treatment (+/- androgen deprivation) or adjuvant radiotherapy treatment after surgery (radical prostatectomy +/- pelvic lymphadenectomy);
- No other synchronous or previous malignant tumor other than skin basal cell carcinoma;
- Patients able to understand and sign the appropriate informed consent;
- Patients able to fill the QoL questionnaire;

Exclusion criteria

- Patients aged less than 18;

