- Patients not eligible for -and actually not submitted to- radical radiotherapy treatment (+/- androgen deprivation) or adjuvant radiotherapy treatment after surgery (radical prostatectomy +/- pelvic lymphadenectomy);
- Low risk prostate cancer (<T2b and T2c or < Gleason Score 7 or PSA value < 10 ng/mL);
- Patients with synchronous or previous malignancy other than skin basal cell carcinoma;
- Patients able to understand and sign the appropriate informed consent (IC) who decide not to subscribe IC;
- Patients not able to understand and sign the appropriate informed consent (IC)

- Patients unable to fill the QoL questionnaire.

Involved Centers

The Radiation Oncology Unit of the University and Spedali Civili of Brescia will be the promoter and coordinator Center. From previous studies of the AIRO Prostate Study Group it can be inferred that at least 15-20 Radiation Oncology Centers from different areas of Italy will be involved; this will assure the widest and homogenous participation throughout the country.

Accrual and timeline

The study will start when a sufficient number of Centres will have obtained EC approval.

Estimated total time of recruitment is 2 years. It will be followed by a three years period of follow up for each patient.

Phase 1: Establishment of the network of Centers involved in the study

During this phase the study protocol has to be shared as much as possible within the Italian radiation oncology community in order to identify and involve as many as possible interested Centres throughout the country.

This will be done in official sessions of the Prostate Cancer Study Group (PCSG) of AIRO meetings.

Each center that will become a part of the study will identify a referring physician who must accomplish the systematic recruitment of eligible patients and provide the collection of data on the appropriate *web portal* established in Brescia.

Phase 2: Activation and recruitment of eligible cases

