Centers involved will identify all the eligible cases with biopsy proven prostate adenocarcinoma. Patients who are candidate to get involved in the study will be contacted by the physician in charge of the study for each Center. **Every** prostate cancer patient consecutively evaluated at the recruiting Centers and planned to receive radical exclusive or post-operative radiotherapy will be registered; this registration includes demographic and staging results data; only intermediate, high, very high patients will have, however, treatment and follow up CRF compiled (both treated with or without ENI; +/- ADT).

Eligible patients will then receive all the information necessary to formulate their adhesion to the study and finally the physician will fill in the “Pretreatment” Case Report Form (CRF) that will include:

- Demographic Information (date of birth, study title, civil state, working information);
- Another person (relatives, friends,...) as a contact to minimize follow up loss;
- Anamnestic data (height, weight, smoking habit, comorbidities, Cumulative Illness Rating Scale [44], Attachment 1);
- Initial diagnosis (date; PSA at diagnosis);
- Risk factors;
- Staging (clinical TNM, date of biopsy, Gleason score, total number of samples, number of positive samples);
- Quality of life and symptoms caused by prostate cancer (using Italian UCLA Prostate Cancer Index) [45, 46];
- General quality of life (SF-12 Standard V1) [47].

The choice of the treatment will be done based on commonly used international guidelines and on the specific internal protocol of each participating Center.

Since this study is observational, involved patients will be treated following *good clinical practice* and institutional policies procedures.

Clinical outcomes, (such as overall survival and biochemical relapse free survival) and variables, demographic features, dosimetric analysis and acute/late toxicities of both RT and ADT will be reported.

Phase 3: Follow-up (1, 3, 6, 12, 18, 24, 30, 36 months)

After the end of the radiotherapy treatment patients will be evaluated 1, 3, 6, 12, 18, 24, 30 and 36 months since the last session.

Every patient will be contacted by the physicians to fill a CRF that will include:

- Vital state (mortality, date and causes of death) or loss to follow up;
- Last PSA value;

- Other treatments (drugs);

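### Use of elective nodal irradiation (aim 1) will be known only for enrolled men at self-selected centres, and the plan cannot show whether that misstates practice

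*Combined protocol and SAP*

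**What the plan says.** **Target.** Aim 1 (Aims of the study) is "To define the diffusion of the practice of treating pelvic lymph-nodes in patients affected by intermediate/high/very high risk non-metastatic prostate cancer", among Italian centres, in men having radical or post-operative radiotherapy. Question 5 (Conclusions, rationale and summary of the study) is a count of centres: "How many Radiation Oncology centers use ENI to treat patients with intermediate/high/very high-risk prostate cancer, with or without ADT".

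**Registration.** Under Phase 2, every consecutive patient planned for radical or post-operative radiotherapy is registered, and "this registration includes demographic and staging results data; only intermediate, high, very high patients will have, however, treatment and follow up CRF compiled". No treatment item is listed for the registration itself.

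**Treatment forms.** The Phase 2 sentence goes on to cover men with and without ENI, and with and without ADT. The synopsis is narrower, both under Inclusion/exclusion criteria and under Visits and exams: "Only intermediate, high, very high patients will have, however, treatment and follow up CRF compiled, based on the inclusion criteria". Those criteria require consent, ability to complete the quality of life questionnaire, and no other malignancy apart from basal cell skin cancer.

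**Where ENI is recorded.** Attachment 1, the pre-treatment form, has the aim of radiotherapy and surgical details but no target volume. Nodal volume first appears in Attachment 2, the 1-month form.

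**Centres.** Phase 1 sets out to "identify and involve as many as possible interested Centres throughout the country", through sessions of the national society's prostate group. At least 15-20 centres are expected.

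**Analysis.** Statistical Considerations gives no estimator or denominator for ENI use and no comparison of enrolled with non-enrolled men.

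**The concern.** A consecutive log of all radiotherapy patients is the right denominator for a question about practice. The plan collects that denominator but leaves out the one item that would supply the numerator. If enrolment is related to the planned volume, the share of enrolled men given ENI differs from the share in the centre's practice, and nothing collected would reveal it.

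Two things are at stake. ENI use is a listed aim, and one purpose of the study is to inform a later randomised trial. The same gap also prevents a direct check of whether enrolment depends on planned treatment, which bears on the ENI comparisons in questions 1 to 3.

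Self-selection of centres is a separate matter. It limits what can be said about Italy, whatever is recorded for each patient.

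**Working it through.** **1. The plan's own figure.** The only precision statement concerns 5-year overall survival: 0.8 with 400 patients. 0.8 ± 1.96 × √(0.8 × 0.2 / 400) = 0.8 ± 0.039, or 0.761 to 0.839, which agrees with the stated 0.76-0.84. It says nothing about ENI use, for which the plan gives no figure.

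**2. Who is in the target, and whose ENI status is recorded.**

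| Men | In aim 1 | Registered | ENI recorded |
|---|---|---|---|
| Eligible risk, enrolled | yes | yes | yes, from the 1-month form |
| Eligible risk, no consent, unable to complete the questionnaire, or other malignancy | yes | yes | no |
| Eligible risk, post-operative salvage | yes | yes | unclear (step 5) |
| Low risk | no | yes | no, and not needed |

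The second row is the gap. The fourth is not a defect, because aim 1 leaves low-risk men out.

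**3. How far the answer can move.** Let q be the ENI share in enrolled men and c the fraction of registered eligible-risk men who enrol. With nothing known about the rest, the share in all of them lies between q × c and q × c + (1 − c). The documents give neither q nor c. Assume q = 0.50:

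- c = 0.90: 0.50 × 0.90 = 0.45, and 0.45 + 0.10 = 0.55, so 45-55%.
- c = 0.70: 0.50 × 0.70 = 0.35, and 0.35 + 0.30 = 0.65, so 35-65%.

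These limits assume nothing about direction. They are extremes, not expected errors.

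**4. Direction.** Let t be the true share, and r1 and r0 the chances of enrolment with and without ENI. The observed share is t × r1 / (t × r1 + (1 − t) × r0). With t = 0.50 assumed:

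- r1 = 0.7, r0 = 0.7: 0.35 / 0.70 = 50.0%, no bias.
- r1 = 0.8, r0 = 0.7: 0.40 / 0.75 = 53.3%.
- r1 = 0.9, r0 = 0.6: 0.45 / 0.75 = 60.0%.
- r1 = 0.6, r0 = 0.8: 0.30 / 0.70 = 42.9%.

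In these scenarios the error runs from about −7 to +10 points and can be zero. The documents do not say which applies.

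**5. Texts that disagree on the population.**

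- Aim 1 and the registration cover post-operative radiotherapy. The inclusion criteria and Attachment 1 name only adjuvant treatment after surgery. Attachment 2 offers post-operative salvage as an aim of radiotherapy, and the Background treats salvage as an alternative to adjuvant treatment. It is unclear whether ENI status will be collected for salvage patients.
- The rationale summary proposes collecting data on patients treated with ENI, whereas Phase 2 takes men with or without it. Read literally, the former fixes the ENI share at 100% and leaves aim 1 unanswerable.

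**The case against.** **The main text may already cover all men at these risk levels.** The Phase 2 sentence mentions only risk group and covers men with and without ENI. It also says what registration includes, which is not a closed list, and no registration form is attached. This is fair as far as it goes. But the synopsis applies the inclusion criteria to the treatment forms, declining consent is an exclusion, and no text puts a nodal item on the log.

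**A reader might infer that ENI use will be overstated,** since centres interested in a study of ENI may use it more. The documents do not support that: they give no ENI rate and no enrolment rate, and the error within centres is zero if enrolment is unrelated to ENI. Nor do they say the result will be published as national practice. The phrase "in a representative sample of intermediate, high and very high risk prostate cancer patients consecutively recruited in Italian Radiation Oncology Centres" refers to survival, toxicity and quality of life data, not ENI use.

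**Question 5 is little affected by non-enrolment.** The forms of enrolled men will usually show whether a centre uses ENI. This stands; for question 5 the limit is self-selection of centres, which extra registration fields would not cure. A confidence interval does not help either: participating centres are fully observed, and volunteers do not support sampling inference to Italy.

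**Some checking is already possible.** Registered staging and demographics allow enrolled and non-enrolled men to be compared on risk profile. That is useful, but it is no check on planned treatment.

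**ENI use is not an endpoint.** Overall survival is primary, and ENI use is not among the secondary endpoints. This stands and limits the weight of the point.

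**Conclusion.** The point holds in limited form. As written, aim 1 can be answered only from enrolled men at self-selected centres. The figure may be too high, too low or right, and the plan can neither detect nor correct an error. The size cannot be derived from the documents. With an assumed 50% in enrolled men, the unresolved range is 45-55% at 90% enrolment and 35-65% at 70%.

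The conclusion rests on reading the synopsis as limiting treatment forms to men who meet the inclusion criteria, and on the registration holding no treatment items beyond those listed. It does not show that ENI use will be misstated, nor that the survival comparisons are biased. This is a cheap improvement to a listed aim and leaves the primary endpoint untouched.

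**What to change.** - **Registration record.** For every registered intermediate, high or very high risk man, add planned pelvic nodal irradiation (yes/no), planned ADT (yes/no), setting, enrolled (yes/no) and reason if not.
- **Analysis.** State that ENI use is reported by centre on that denominator, and compare planned ENI between enrolled and non-enrolled men. This removes the range in working step 3 within participating centres.
- **Scope.** Word aim 1 and question 5 as applying to participating centres.
- **Reconcile.** Settle whether post-operative salvage patients are included (aim 1, registration, inclusion criteria, Attachments 1 and 2), and whether the cohort is ENI-treated men only or men with and without ENI (rationale summary, Phase 2).

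The cost is a few fields on a log the plan already keeps, one comparison and some wording. There are two downsides. The legal basis for registering men who do not consent must cover the added fields, which has to be settled before they are used. For non-enrolled men the log would hold planned rather than delivered irradiation, so the report should say which is shown; in enrolled men the plan can be checked against the volume on the 1-month form.

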- Quality of life and complications due to prostate cancer (Italian UCLA-PCI) [45, 46];
- General quality of life (SF-12 Standard V1) [47].

The Italian UCLA-PCI and SF-12 Standard V1 questionnaires reported in Attachment 2 and Attachment 3 [45, 46, 47] will be given by the referring physician and self-compiled by patients in physician's absence, eventually with the help of a nurse if necessary; thereafter, the referring physician will insert the data to the database.

Data Collection, Confidentiality

Data will be collected through an *ad hoc* web based software, built to guarantee:

1. Respect of the Italian laws and of the international rules about GMP and privacy, according also to the general principles fixed by the Helsinki declaration and its subsequent updates;
2. The anonymization of the patient records;
3. The possibility for each participating Center to have unrestricted access to its own data;
4. The restriction of the access to the full dataset composed by the sum of the records provided by the single Centers; this will be allowed only after the authorization of the PI and the Study Coordinator. Once the study will be completed, access to the whole database will be possible only after having obtained the authorization of the AIRO President in charge and of the AIRO Board;
5. The safe storage of the data, along with that of the previous AIRO-PCSG studies, along with.

The use of the software will be elucidated to the single participating Centers in *ad hoc* start up

meetings, to guarantee an appropriate and homogeneous data collection; a tool bar will however be devised, to automatically verify inconsistencies in the data collected.

Statistical Considerations

Sample size

From previous experiences of the AIRO PCSG [49, 50], at least 15-20 Radiotherapy Centers from different regions of the country will be able to participate to the study. It is conceivable an accrual of at least 400-500 patients within 2 years and a further follow up of at least 3 years for each patient. For intermediate and high risk patients, an overall survival at 5 years of 0.8 has been previously reported (RTOG 94-13) [51]. According to the primary end-point of the study, a sample size of 400 patients will allow to estimate a 5-year survival of 0.8 with 95% confidence interval of 0.76-0.84 [52].

Statistical Analyses

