In order to describe the data, mean and standard deviation will be used for normally distributed continuous variables, median and ranges for non-normally distributed continuous variables, proportions and percentages for categorical variables. Associations between two categorical variables will be assessed through the Pearson's chi-squared test or Fisher test, when appropriate. Differences between two-sample central tendencies will be assessed with a two independent sample t-test or Mann-Whitney U test or Wilcoxon, depending on distribution of the continuous variable.

Analysis of variance and covariance and regression models will be used for evaluating the associations of some variables with survival taking account of possible confounders.

In order to compare groups in terms of survival end-points, Kaplan-Meier curves will be estimated and log-rank tests will be performed.

Periodical analyses are planned in order to check the quality of entered data.

The analyses will be performed by using STATA 13 (StataCorp. 2013. Stata Statistical Software: Release 13. College Station, TX: StataCorp LP) or SPSS Statistical Software.

Ethical committee

After the final approval by the AIRO-PCSG, the Protocol will be submitted to the Ethical Committee (EC) of the Study Coordinating Centre; when it will be approved, the single participating Centres will consequently apply for approval of their EC. According to the judgment of the PI and of the Study Coordinator, the first patient will be enrolled when a sufficient number of Centres will have obtained EC approval. This will be the starting date for the study.

The present study will be performed in accordance with the present protocol, with the principles of Good Clinical Practice in the respect of the ICH GCP guidelines and the ethical principles contained in the Helsinki declaration.

Publication rules

Interim and final results of the study will be published under the final responsibility of the PI and of the Study Coordinator.

The following publication rules will be enforced:

1. The participating Centers should approve the paper;
2. Only Centers contributing to more than 5% of the cases collected will have a person quoted as Author of the paper; however, every Center contributing to the common database, as well as the people working to realize the Study, will be publicly quoted and their contribution acknowledged in the paper;
3. Authorship is granted in proportion to:
 - a. the cases contributed to the database;

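### ENI and ADT use may cluster by centre, but no planned comparison names centre, so centre differences may pass for treatment effects and p-values may be too small

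*Combined protocol and SAP*

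**What the plan says.** Phase 2 of the protocol (and Visits and exams in the synopsis) says of treatment: "The choice of the treatment will be done based on commonly used international guidelines and on the specific internal protocol of each participating Center". It adds that patients are managed under "institutional policies procedures". Question 5 of the rationale treats ENI as something a centre does or does not do: "How many Radiation Oncology centers use ENI to treat patients".

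Involved Centers expects that "at least 15-20 Radiation Oncology Centers from different areas of Italy will be involved", and Sample size foresees "an accrual of at least 400-500 patients within 2 years".

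For group comparisons of survival, Statistical Analyses says that "Kaplan-Meier curves will be estimated and log-rank tests will be performed". For categorical outcomes: "Associations between two categorical variables will be assessed through the Pearson's chi-squared test or Fisher test, when appropriate". Continuous outcomes get a two-sample t-test or a rank test. Regression is also planned, for associations with survival, adjusting for confounders that are not listed. Centre does not appear in that section as a stratum, covariate, random effect or cluster.

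**The concern.** Centre policy is one of the two stated drivers of treatment. If it matters in practice, men in the same centre will tend to share their ENI and ADT status. They will also share local case mix, technique and the physicians who grade toxicity. Two separate problems follow.

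- **Confounding.** A difference between centres that use ENI often and centres that use it rarely may be read as an effect of ENI.
- **Variance.** Tests that count each man as independent overstate the information in the contrast.

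Toxicity and quality-of-life comparisons are the most exposed, because the adjusted analysis is planned for survival only. What is at stake is the use made of the results. Questions 1 to 4 ask about benefit and toxicity of ENI, and aim 6 uses the data to decide whether a randomised trial is needed and what it should look like.

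**Working it through.** **Inputs from the documents.** 400 to 500 men; 15 to 20 centres; 5-year overall survival 0.8; at least 3 years of follow-up per man.

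**Assumptions, not in the documents.** Two-sided 5% tests, equal centre sizes, and an intra-centre correlation (ICC) of 0.01 to 0.05.

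**Step 1: the plan's own figure.** 0.8 ± 1.96 × √(0.8 × 0.2 / 400) = 0.8 ± 0.039, or 0.761 to 0.839. This reproduces the stated 0.76 to 0.84. It assumes independent men and complete 5-year follow-up.

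**Step 2: ENI fixed by centre.** Mean centre size m = men / centres. Design effect DE = 1 + (m − 1) × ICC. True error = 2 × [1 − Φ(1.96 / √DE)].

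| Men / centres | m | ICC 0.01: DE, error | ICC 0.02: DE, error | ICC 0.05: DE, error |
|---|---|---|---|---|
| 400 / 20 | 20.0 | 1.19, 7.2% | 1.38, 9.5% | 1.95, 16.0% |
| 500 / 20 | 25.0 | 1.24, 7.8% | 1.48, 10.7% | 2.20, 18.6% |
| 400 / 15 | 26.7 | 1.26, 8.0% | 1.51, 11.1% | 2.28, 19.5% |
| 500 / 15 | 33.3 | 1.32, 8.8% | 1.65, 12.7% | 2.62, 22.6% |

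**Step 3: weaker clustering, by simulation.** Log-rank tests were simulated with no true ENI effect. Survival was exponential with 5-year survival 0.8, censoring was uniform between 3 and 5 years, and centres had a gamma frailty. There were 1,500 runs per setting, so the Monte Carlo standard error near 5% is √(0.05 × 0.95 / 1500) = 0.6 percentage points. Each cell gives the rejection rate (%) at frailty variance 0.1 / 0.2 / 0.4.

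| ENI use | 20 centres, 400 men | 15 centres, 495 men |
|---|---|---|
| All or none by centre, plain log-rank | 7.9 / 11.8 / 18.5 | 10.8 / 19.8 / 25.0 |
| 20% or 80% by centre, plain log-rank | 6.3 / 6.7 / 9.5 | 6.1 / 8.4 / 11.4 |
| 20% or 80% by centre, stratified by centre | 4.9 / 5.3 / 4.7 | 4.9 / 4.5 / 5.2 |
| 50% in every centre, plain log-rank | 4.1 / 4.3 / 4.4 | 5.5 / 6.5 / 5.1 |

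With no centre effect the plain test rejects in 4.3% to 5.9% of runs. The single 6.5% in the last row is not a clustering signal: the stratified test gave 6.4% in the same runs. At frailty variance 0.1 the 20%/80% rates are barely above 5%.

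**Step 4: the pooled interval.** With 400 men the half-width of 0.039 is multiplied by √DE. It becomes 0.043 to 0.044 at ICC 0.01 and 0.055 to 0.059 at ICC 0.05.

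**Step 5: what a within-centre survival estimate can offer.** Under a constant hazard, 3-year survival is 0.8^(3/5) = 0.875. A centre of 20 to 33 men then has about 2.5 to 4 deaths by 3 years.

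**The case against.** A reader might infer that ENI, technique and ADT arrive as fixed centre packages, and hence that the p-values are certainly too small. The documents do not support this. The sentence on treatment choice names international guidelines as well as the centre's protocol, and the Background ties ADT to patient risk, which varies within a centre. Nowhere is it said that some centres treat nodes in nearly all men and others in nearly none. If ENI varies freely within centres, the simulation shows no material inflation.

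The regression could include centre. That is true, but centre is not named and the sentence covers survival only.

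Much of what differs between centres is recorded per patient. Attachment 2 captures image guidance, technique, dose, volumes, organ dosimetry and hormonal therapy; Attachment 1 captures comorbidity, PSA, stage and Gleason score. These can be adjusted for, and this stands in part: what remains is unmeasured difference between centres. Grading habits cannot affect overall survival, patients complete the quality-of-life forms themselves, and common grade definitions help for toxicity. But several toxicity grades rest on judgement (small bleeding, severe symptoms), so local habits can still matter.

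The sample size is for one pooled estimate, and no comparison has a stated alpha, power or primary status. This also stands, and it limits the consequence. The group tests are nevertheless planned, and the pooled interval widens too.

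A reader might also infer that question 5 cannot be answered because no centre policy is recorded. It can be answered for participating centres, by tabulating the recorded target volumes by centre.

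**Conclusion.** The gap is real and its size is conditional. Statistical Analyses names no method that accounts for centre, although centre policy is a stated driver of treatment.

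- If ENI is fixed by centre, the true error at nominal 5% is about 7% to 9% at ICC 0.01 and 16% to 23% at ICC 0.05.
- If centres use ENI in 20% or 80% of men, it is about 6% to 11% for frailty variances of 0.1 to 0.4.
- If ENI varies freely within centres, it is about nominal.

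The ICC, the frailty variance, equal centre sizes and the ENI share by centre are all assumptions. Confounding by centre is a separate matter: no standard-error correction removes it. The point does not invalidate the study's main descriptive estimate. It is a cheap improvement to make before the data are analysed.

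**What to change.** In Statistical Analyses, state that every ENI or ADT comparison of survival, toxicity and quality of life accounts for centre:

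1. Where centres treat men both ways, use a centre-stratified log-rank test and Cox model for survival, and Mantel-Haenszel methods or regression with centre for toxicity and quality of life.
2. For the overall estimate, use a centre random effect (shared frailty for survival) or cluster-robust standard errors, with a correction for only 15 to 20 clusters. These address the variance; they do not by themselves remove centre confounding.
3. Show the within-centre estimate next to the overall one.
4. Tabulate ENI and ADT use by centre from the recorded target volumes and hormonal therapy. This also answers question 5 for participating centres.
5. State that if ENI proves nearly all-or-none by centre, the contrast rests on 15 to 20 clusters and cannot be separated from centre.

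The cost is wording. Centre must already be identifiable, because the Publication rules tie authorship to each centre's share of cases. The downsides are wider intervals and, given about 2.5 to 4 deaths per centre by 3 years, an imprecise within-centre survival estimate. Recording each centre's written ENI policy at start-up would be a useful but optional extra.
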